6.2 Clinical and Laboratory Evaluations (if applicable)

6.2.1 HemaSpot Testing

 HIV-positive participants submit HemaSpot devices by mail for viral load testing at baseline, 6- and 12-month follow-up points.

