10.2 Power Estimates

The primary outcome for the proposed trial is stratified by HIV status and defined as *successful* engagement in care. For HIV-positive participants at baseline, we define successful engagement in HIV care as consistent VS across the 12-month trial (per IOM guidelines²¹⁸). For HIV-negative

or sero-unknown at baseline, we define successful engagement in care as participation in routine HIV testing (2 HIV tests with at least 3 months apart from one another, per CDC guidelines²¹⁹). We define power as correctly identifying the difference in the proportions of YBLMT with serospecific engagement in HIV care within 12 months of each intervention arm (2 arms: HMP Stigma with researcher-created network, HMP Stigma with peer-referred network) to the control arm (Information Control), thus powering for 3 independent hypothesis tests. Our sample size calculations are based on pair-wise HIV-stratified comparisons of the 3 groups in terms of proportion of successful engagement using a two-sided significance level of 0.05 altered by the number of comparisons using a Bonferroni adjustment (significance level is 0.017 for 3 comparisons). To have 80% power to detect a minimum effect size (OR=1.9) of successful engagement in care between the 3-arm trial, we will require at least 450 HIV-negative and 450 HIV-positive participants to detect a 17% difference in successful engagement in. In the event of a 20% loss to follow-up, we will have sufficient power to detect an OR=2.1 (18% difference) at alpha=.017. Participants may continue the study even if they miss an assessment intermittently. We will compare those who completed different follow-up interviews with those who did not on key baseline predictors to check for possible sampling bias. Our analysis will use ITT as appropriate.

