10.4 Missing Data

Several procedures will be used to conduct data analysis when data for either outcomes or covariates are missing. The first step will be to assess the extent and pattern of missing data. If data are missing for only a few cases, then data analysis will be conducted only on study participants with complete data. However, when such a strategy would result in loss of data from a substantial proportion of participants, or if this approach would lead to biased or inaccurate results, then some form of imputation will be performed. The form of imputation used will depend on the nature of the data that are missing. For example, data that are collected repeatedly might be imputed using the "last value carried forward" method; and in some instances, interpolation between neighboring points might also be used.

When the primary endpoint is missing, one data analysis will be conducted using only cases with the endpoint. Subsequent analysis will be done where missing endpoints are imputed. Hot-deck imputation or regression imputation may also be used in this context.

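### The loss scenario in section 10.2 does not deliver its stated power for OR=2.1 (at most about 68% at 120 per arm), and a person-level 20% allowance does not cover an HIV-positive endpoint built from repeated mailed kits

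*Combined protocol and SAP*

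**What the plan says.** Section 3.2 randomises 150 HIV-positive participants to each of three arms. Section 10.2 bases the sample size on pairwise comparisons within HIV stratum, "using a two-sided significance level of 0.05 altered by the number of comparisons using a Bonferroni adjustment" ("significance level is 0.017 for 3 comparisons"). For 80% power at OR=1.9 it states that "we will require at least 450 HIV-negative and 450 HIV-positive participants to detect a 17% difference". It then gives the loss scenario: "In the event of a 20% loss to follow-up, we will have sufficient power to detect an OR=2.1 (18% difference) at alpha=.017". Its next sentence reads "Participants may continue the study even if they miss an assessment intermittently".

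The HIV-positive primary endpoint is consistent viral suppression over 12 months. Section 6.2.1 gives the source of the data: "HIV-positive participants submit HemaSpot devices by mail for viral load testing at baseline, 6- and 12-month follow-up points". Section 5.4.2 expects some samples to be unprocessable and offers a replacement only to participants who viewed the instructional video. On missing endpoints, section 10.4 says "When the primary endpoint is missing, one data analysis will be conducted using only cases with the endpoint" and adds that a later analysis will impute them. The only retention target, in section 8.1, is at least 80% at the 3-month assessment, when no kit is due.

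**The concern.** There are two linked problems. First, the power claimed after 20% loss does not follow from the stated test, sample size and significance level. Second, the allowance is a single reduction in people. A participant can be confirmed as consistently suppressed only if every required kit comes back and can be processed. When misses are spread over different people at different visits, the share with a complete set is lower than the share returned at any one visit. The trial could see 80% kit return at each visit, appear to be within its allowance, and have fewer than 120 determinable endpoints per arm. A null result in the HIV-positive stratum could then be read as stronger evidence of no effect than it is.

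**Working it through.** **Inputs from the documents.** 150 per arm (3.2); 20% loss, OR=2.1, 18% difference, two-sided alpha 0.017, pairwise tests (10.2); kits at baseline, 6 and 12 months (6.2.1). The control rate, the kit-return rate, the number of viral loads that consistency requires and the scoring of a missing one are not in the text available.

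**1. The plan's own figure.** The normal approximation with pooled null variance gives, with n per arm, control rate p0, intervention rate p1 and mean rate p̄:

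power = Φ{ [ (p1 − p0) − z·√(2p̄(1−p̄)/n) ] / √( [p0(1−p0) + p1(1−p1)]/n ) }, with z = 2.387 for two-sided 0.017.

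The control rate was varied from 0.05 to 0.80. Power for OR=2.1 is highest at about p0 = 0.41:
- Control odds 0.41/0.59 = 0.695; multiplied by 2.1 they are 1.459, so p1 = 0.593 and the difference is 0.183. This agrees with the stated 18%.
- n = 150 × 0.80 = 120. Null standard error 0.0645; alternative standard error 0.0635.
- (0.1834 − 2.387 × 0.0645)/0.0635 ≈ 0.46, so power is **67.8%**.

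This is the best case. At n = 120, power is 60.1% with p0 = 0.60 and 49.9% with p0 = 0.70. The odds ratio giving 80% power is at least **2.32**. With two-sided 0.05 and no Bonferroni adjustment, the maximum is 81.5%, which is close to the claim, but that is not the stated test.

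**2. Complete kit sets.** Assume that 20% of kits are missing or unusable at each required visit.

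| Pattern of misses | Two kits | Three kits |
|---|---|---|
| Independent | 150 × 0.8² = 96 | 150 × 0.8³ = 77 |
| Within-person correlation 0.5 | 150 × 0.72 = 108 | 150 × 0.672 ≈ 101 |
| Same people at every visit | 120 | 120 |

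At 10% missing per kit with independent misses, 150 × 0.9² = 121.5 or 150 × 0.9³ = 109 remain. With independent misses, 120 per arm is kept only if per-kit success is at least √0.8 = 0.894 (two kits) or the cube root of 0.8 = 0.928 (three kits).

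**3. Determinable endpoints.** One observed unsuppressed kit already rules out consistent suppression, so only successes need every kit. Let p be the true success rate, q = 0.8 and k the number of kits, with misses independent.
- Determined successes: p·q^k.
- Determined failures, if suppression is the same at every visit: (1−p)·[1 − (1−q)^k].
- Determined failures, if suppression is independent between visits with s = p^(1/k): 1 − [1 − q(1−s)]^k.

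Example with two kits and the same status at every visit: control 0.41 × 0.64 + 0.59 × 0.96 = 0.829, or 124 of 150; intervention 0.593 × 0.64 + 0.407 × 0.96 = 0.770, or about 116.

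| Kits | Suppression between visits | Control n | Intervention n | Power |
|---|---|---|---|---|
| 2 | same status | 124 | 116 | 65.7% |
| 2 | independent | 113 | 107 | 64.9% |
| 3 | same status | 119 | 106 | 59.2% |
| 3 | independent | 106 | 96 | 58.9% |

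The odds ratio stays at 2.10 to 2.15. Against 67.8%, the loss is 2.1 to 8.9 points. These powers are not read off n alone: the rule keeps more failures than successes, so the success rate among determinable controls falls from 41% to between 26% and 35%.

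**4. Equal-arm table at the most favourable control rate.**

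| Determinable per arm | Power for OR=2.1 | OR for 80% power |
|---|---|---|
| 120 | 68% | 2.3 |
| 108 | 62% | 2.4 |
| 96 | 56% | 2.6 |

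**The case against.** Section 10.2 speaks of loss of people, and 20% per kit is not its figure. If 20% already means everyone without a usable endpoint by month 12, then 120 per arm is right, and the implied independent loss per kit is about 10.6% (two kits) or 7.2% (three). This stands: the kit calculation is a sensitivity range and does not show an error in the number 120.

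A reader might infer that the evaluable sample drops to 77 per arm and that 22 points of power are lost (67.8% to 45.5%). The documents do not support that. It needs three required kits, independent misses, 20% loss per kit and the discarding of participants already known to have failed. A reader might also infer that only complete cases will be analysed, but section 10.4 also plans imputation and section 10.2 mentions ITT as appropriate. Replacement kits and the payment per returned kit (5.4.2, 8.2) should limit losses. Table 2, to which section 5.4.4 refers for the outcomes, is not in the text available, so the number of kits required is an inference.

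None of this rescues the claim for OR=2.1. At 120 per arm with no further loss, the stated pairwise test still gives at most 68%.

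**Conclusion.** The point holds in two parts of different strength. The shortfall at 120 per arm rests on the plan's own inputs: power for OR=2.1 is at most about 68%, and the detectable odds ratio is at least about 2.3, whatever the control rate. The kit-level part is conditional. With 20% of kits missing at each visit, complete sets number 77 to 120 per arm. With observed failures counted and independent misses, about 96 to 124 per arm are determinable and power is about 59% to 66%, a further loss of about 2 to 9 points. That range assumes a control rate of 0.41 and misses that are unrelated to suppression and equally frequent in both arms. The further loss is measured from 68%; it should not be read as a fall from 80%.

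**What to change.** - In section 10.2, define the loss allowance as the proportion of participants without a determinable primary endpoint. State how many kits are required, that success needs all of them suppressed, and that any observed unsuppressed kit is a failure. A requirement that all kits be returned should not be used as the definition, because it discards known failures.
- Replace the OR=2.1 claim for the HIV-positive stratum with the table in step 4 of the working, or its equivalent. State the assumed control rate, which under this scoring is the rate among determinable participants, and the assumed kit-return rate.
- Add the proportion with a determinable endpoint, by arm, to the DSMB report.

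This takes a few sentences, one small table and one reporting line. It needs no extra participants, kits or staff. The only downside is that the stated power becomes less favourable.

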10.3 Statistical Analysis Plan

10.3.1 Specific Aim 1:

Specific Aim 1 is to test whether a smartphone application (app) intervention (HMP Stigma) that promotes user-generated content and engagement to address intersectional stigma is associated with successful engagement in care as compared to an information-only control arm consisting of online informational articles and resources curated for YBLMT. Clinical and demographic characteristics will be described for the entire sample, and by treatment group. These will be compared between treatment groups using ANOVA or Kruskal-Wallis test for continuous variables, and chi-square tests for categorical variables. We will conduct primary analyses of our successful engagement in care outcome using logistic regression analyses to compare each active treatment group to the control in pairwise comparison tests at an adjusted significance level of 0.017 to reduce Type-I errors in our 3-arm trial. This approach allows us to also test for differential efficacy between the two intervention conditions (i.e., Does peer-referral HMP outperform the researcher-created HMP arm?).

Logistic regression analyses will be stratified by serostatus. The regression will be run with group assignment only in the model. Among HIV-positive participants, we will examine how intervention conditions influence YBLMT's likelihood of consistent VS over 12 months. We will also test intervention effects on retention in care per IOM guidelines (i.e., proportion of HIV-positive participants who obtain at least 2 viral load tests (at least 3 months apart) within 12 months). For HIV-negative YBLMT, we will compare the proportion of participants who obtain at least 2 HIV tests (at least 3 months apart) within 12 months across arms. Estimates will be calculated and presented with corresponding 95% exact binomial confidence intervals. In secondary outcome analyses, we will compare arms across other HIV care continuum outcomes, as well as stigmarelated (e.g., reduction in HIV-related stigma) outcomes, using a logistic regression with group assignment on the model assuming no imbalances due to successful randomization.

10.3.2 Specific Aim 2:

Specific Aim 2 is to explore whether user engagement, as measured by paradata, mediates the intervention effects observed in stigma and HIV care outcomes.

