5.0 STUDY PROCEDURES

5.1 Enrollment Procedures

We will enroll a total of 750 participants. Of these participants, 300 will be HIV-negative and 450 will be HIV-positive. After participants are consented, participants will complete a baseline CASI survey and then will be randomized into the Tailored Information-Only Control (Attention Control), Researcher-Created HMP Network (Intervention Arm 1), or HMP with Peer-Referral Network (Intervention Arm 2). Intervention Arm 2 will only have 150 HIV-positive participants randomized to it, as the remaining participants will be peers who are referred by their peers and enroll if eligible. Upon enrollment, all participants will be provided a link to access the HMP app through the Apple App Store or the Google Play Store for Android. Once downloaded, participants will create their app account by entering their email address, creating a username, password, and PIN, entering their mailing address, opting in or out of notifications, and selecting an avatar.

Those randomized in the Tailored Information-Only Control (Attention Control) will be given a streamlined version of the app. They will have access to the Care Locator and Knowledge Center articles and be able to message the Care Navigator. HIV-negative and sero-unknown participants will be able to request HIV home test kits. HIV-positive participants will be sent HemaSpot devices at Baseline, 6 months, and 12 months. They will not have access to the interactive forums, activities, or the Ask and Expert feature.

Those randomized in the Researcher-Created HMP Network (Intervention Arm 1) will have access to the full HMP app, including access to the Arm 1 Forum in which participants will be able to create threads and comment on any threads in the forum, whether moderator- or usergenerated.

Those randomized to the Peer-Referral Network (Intervention Arm 2) will have access to the full HMP app, including access to the Arm 2 Forum in which participants will be able to create threads and comment on any threads in the forum, whether moderator- or user-generated. The only difference between this version and the Intervention Arm 1, is that two thirds of the users (300) that comprise this group are added by peer referral by the 150 participants who were randomized into this arm.

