10.3.2.1 Quantitative Analyses

Building our theoretical framework, we will use structural equation modeling (SEM) to test whether engagement with stigma content predicts changes in stigma-related outcomes over time (e.g., decreases in anticipated HIV stigma), and changes in HIV care outcomes over time (e.g., repeat HIV testing; consistent VS). In these HIV-stratified analyses, we will use latent class analysis to characterize users' engagement in the app. We will estimate the independent contributions of passive and active engagement on both stigma and HIV outcomes, as well as how cumulative engagement in stigma-related discussions influences these outcomes. Key sociodemographic predictors will be included as covariates (e.g., age, time since diagnosis). We will also examine the contribution of specific mediators (e.g., social support) in these models by decomposing the total effects into direct and indirect effects. In exploratory analyses, we will use multigroup SEM analyses to test whether these proposed models differ based on latent classes of users (e.g., active forum contributors vs. lurkers; low, moderate, high engagement). Multigroup analyses allow us to compare the strength and direction of the effect sizes in our models and their overall fit across these engagement groups. Ideal models will have values of .90 or higher among fit indices and values of .06 or lower for RMSEA as acceptable indicators.85 The proposed study has sufficient power to carry out these subsample analyses in our model identification and model testing stages. MacCallum et al.²²⁰ show that power of .80 is achievable with alpha=.05 and 30 degrees of freedom in cross-sectional analyses with a sample of 366 for a close model fit (for df=100 the minimum sample size is 178). Thus, we have ample power for these SEM analyses, even when dividing the sample by HIV status or engagement profile.

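### The primary logistic model contains arm only; prespecified pre-randomisation covariates would add precision at almost no cost, by an amount the documents do not fix

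*Combined protocol and SAP*

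**What the plan says.** - Section 10.3.1 (Specific Aim 1) fits logistic regression separately by serostatus, and "The regression will be run with group assignment only in the model". For the secondary outcomes it gives the reason: "assuming no imbalances due to successful randomization". It also tests baseline characteristics between arms, but states no rule for acting on the result.
- Section 10.2 sets the level: "two-sided significance level of 0.05 altered by the number of comparisons using a Bonferroni adjustment", that is, "significance level is 0.017 for 3 comparisons". The planning statement begins "To have 80% power to detect a minimum effect size (OR=1.9". Section 3.2 gives 150 randomised per arm: three arms in the HIV-positive stratum, and control and Arm 1 only in the HIV-negative/unknown stratum.
- Baseline information: under section 5.1, "participants will complete a baseline CASI survey and then will be randomized". Under section 6.2.1, "HIV-positive participants submit HemaSpot devices by mail for viral load testing at baseline, 6- and 12-month follow-up points".
- Covariates appear only in the later aims. Section 10.3.2.1 says "Key sociodemographic predictors will be included as covariates (e.g., age, time since diagnosis", and section 10.3.3 adds network covariates.

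**The concern.** Randomisation answers bias, not precision. A baseline variable that predicts the outcome raises the power of the arm comparison at the same sample size and type I error. Randomisation is stratified only by HIV status (section 5.3), so nothing in the design balances earlier suppression or testing behaviour between arms. If a chance imbalance shows up in the planned baseline tests, any adjustment would be post hoc.

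The contrasts are tested at 0.017 with 150 per arm, where power is already tight. Giving away precision that costs no recruitment therefore matters.

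**Working it through.** **Inputs from the documents.** 150 per arm, two-sided 0.017 (z = 2.387), OR 1.9, 80% power. The control success rate, the baseline suppression rate and the strength of any covariate are not given; they are assumed and varied below.

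**1. The plan's own figure.** Power ≈ Φ(ln OR / SE − z), with SE² = 1/[n·p1(1−p1)] + 1/[n·p2(1−p2)]. The best case for OR 1.9 is near p1 = 0.42, p2 = 0.579:
- SE = √(1/36.5 + 1/36.6) = 0.234.
- ln 1.9 / SE = 0.642/0.234 = 2.74.
- Power = Φ(2.74 − 2.387) = 64%.

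The pooled two-proportion test gives at most 65% at any control rate. The stated 80% is not reproduced at 0.017; at 0.05 the same test gives at most 79.0%. This shortfall is a separate matter, but it shows that there is no power to spare.

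**2. Effect of adjusting for one binary baseline covariate.** The marginal OR is held at 1.9. A conditional log OR t, common to both covariate levels, is solved so that the marginal rates are preserved. Then information = Σ v0·v1/(v0+v1) over covariate levels, where v = n·p(1−p) in each arm, and power = Φ(t·√information − z).

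Worked case: 60% suppressed at baseline; later sustained suppression in 70% of those and 20% of the rest.
- Control rate = 0.6×0.7 + 0.4×0.2 = 0.50; intervention rate = 1.9/2.9 = 0.655.
- Unadjusted: SE 0.237, power 62.6%.
- Adjusted: t = 0.853 (conditional OR 2.35). Rates under intervention are 0.846 and 0.370, and 0.6×0.846 + 0.4×0.370 = 0.655, as required.
- Information = (18.9×11.75)/30.65 + (9.6×13.98)/23.58 = 7.25 + 5.69 = 12.94, so SE = 0.278.
- Power = Φ(0.853/0.278 − 2.387) = 75.2%, a gain of 12.6 points.

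Same method, 60% suppressed at baseline. The last column assumes 30% of baseline kits missing at random, handled by a missing-indicator:

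| Later suppression: suppressed / not at baseline | Covariate OR | Arm only | Adjusted | Gain | Gain, 30% missing |
|---|---|---|---|---|---|
| 60% / 30% | 3.5 | 63.2% | 67.5% | 4.3 | 3.0 |
| 60% / 20% | 6.0 | 63.9% | 72.2% | 8.3 | 5.7 |
| 70% / 20% | 9.3 | 62.6% | 75.2% | 12.6 | 8.6 |
| 80% / 20% | 16 | 59.9% | 77.9% | 18.0 | 12.3 |
| 80% / 10% | 36 | 61.9% | 87.0% | 25.1 | 17.8 |

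Simulation (3,000 trials per cell) gives about 4 points in the top row and 29 in the bottom row (about 3 and 20 with missing kits). The range is summarised as about 5 to 27 points (about 3 to 18 with missing kits); its ends are good to two or three points. In a null run of 5,000 trials (70% / 20%), rejection was 1.6% unadjusted and 1.5% adjusted against a nominal 1.7%.

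**3. Weak to moderate covariates.** With a control rate of 42% and covariate prevalence 60%, power rises from 64.0% to 64.4% (covariate OR 1.5), 65.3% (OR 2) and 67.2% (OR 3). This is about 0.4 to 3 points.

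**4. Is baseline suppression usable?**
- Timing: section 5.1 runs consent, survey, randomisation, app download, then entry of a mailing address in the app. Section 5.2 asks for the address after download so that the kit can be sent, and section 8.2 allows 45 days from receipt for the return incentive. The baseline sample is therefore probably taken after assignment.
- Endpoint: section 10.2 does not say whether the baseline sample counts towards consistent suppression. If it does, nobody unsuppressed at baseline can succeed, and a logistic model with that covariate has separation.

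**The case against.** The strongest reply is that this is efficiency, not error. The arm-only test is prespecified, valid in the randomised contrasts and already split by the randomisation stratifier, and section 10.3.3 provides for a separate analysis plan in which changes can be justified. All of that stands, and it limits the point to a recommended improvement.

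A reader might infer three stronger things that the documents do not support.
- *That a definite amount of power, such as 6 to 20 points, is lost in all the randomised contrasts.* The documents give no control rate, baseline suppression rate or covariate association. The HIV-negative contrast has no baseline viral load, and neither the survey instrument nor the table of measures is in the available text.
- *That the baseline viral load is a ready pre-randomisation covariate.* Only the survey is shown to precede randomisation. If kits are returned after arm-specific app access, both the value and its missingness could depend on arm. Adjusting for them could then bias a test that is valid as it stands.
- *That the primary analysis is biased without covariates.* It is not, in the randomised contrasts.

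**Conclusion.** The point holds as a loss of precision. Section 10.3.1 omits prognostic baseline information that the trial collects, and no adjusted model is planned even as a sensitivity analysis.

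The large gains belong to the HIV-positive stratum and need three conditions: an endpoint read on months 6 and 12, a kit collected before arm could affect it, and strong prognosis. The assumed inputs are 50–70% suppressed at baseline, then sustained suppression in 60–80% of those and 10–30% of the rest. If only survey covariates are usable and they are weak to moderate, the gain is small. Adjustment should not be counted on to restore the planned 80%.

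**What to change.** In section 10.3.1, for each serostatus stratum and the randomised contrasts:
- Make the primary model arm plus a small prespecified set of covariates from the pre-randomisation survey. HIV-positive: age, time since diagnosis and, if asked, self-reported suppression or adherence. HIV-negative/unknown: age and, if asked, HIV testing before entry.
- Report a standardised risk difference alongside the adjusted OR.
- Keep the arm-only model as a sensitivity analysis.
- Add HemaSpot baseline suppression only if the endpoint is read on months 6 and 12 and the sample was collected before assignment or app access, or within a prespecified window judged unaffected by arm. State the rule for missing kits.

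The cost is analysis-plan wording, fixed before outcomes are seen, plus a decision on the endpoint and on kit timing if viral load is to be used. One small downside: the adjusted OR is conditional (2.35 against a marginal 1.9 in the worked case) and is not numerically comparable with the planning OR, which is why the standardised risk difference is needed.

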Multiple stigmas related to sexuality, race, and HIV infection negatively impact HIV testing, engagement in HIV care, and consistent viral suppression (VS) among young Black or Latino men who have sex with men and transgender women (YBLMT). At present, few interventions have addressed the effects of intersectional stigma among HIV-infected and uninfected populations. In response to the National Institutes of Health RFA-MH-18-606, this study tests whether a smartphone application (app) intervention tailored for intersectional stigma amelioration can elicit online social support, promote intervention engagement, and mitigate the impact of multiple stigmas on HIV-related outcomes. We will recruit and enroll 1,050 young (ages 15-29), racially and ethnically diverse men who have sex with men and transgender women affected by HIV across the United States. Using a HIV-status stratified randomized trial design, participants will be assigned into one of three conditions (information-only control, a researcher-driven social network intervention, or a peer-referred social network intervention). Behavioral assessments will occur at baseline, 3, 6, 9 and 12 months; biomarkers (viral load) are scheduled for baseline, 6 and 12 months (for HIV-positive participants). HIV negative/status unknown participants may order through the app up to 3 HIV OraQuick self-tests.

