2.3 Study Hypotheses/Research Questions

Our proposal is built on the scientific premise that network interventions can encourage behavior change. ^{31,90-95} Given that YBLMT widely use social networking sites and applications (apps) to socialize with similar others, ^{28,48,76} HMP Stigma seeks to promote social support by creating a virtual community for YBLMT; thus, we hypothesize that:

A. Compared to YBLMT assigned to an information-only condition, YBLMT assigned to HMP Stigma will report greater reductions in stigma, and be more successful at buffering the negative sequelae of intersectional stigma and circumventing barriers to successful engagement in the HIV care continuum.^{71,96}

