5.4.4 Surveys

As noted in Table 2, we include a summary of the primary and secondary outcomes, key intervention mechanisms of change, and potential covariates. Assessments will not take more than 50 minutes to complete. We have taken several steps to ensure that the assessments are developmentally appropriate. Consistent with best practices, we will use validated measures developed as part of the NIH Adolescent Medicine Trials Network (ATN) for HIV/AIDS

Interventions studies. We will use gate-keeping questions to decide whether participants should receive other probes within a domain. For example, a participant who has not reported lifetime substance use will not be asked additional substance use questions.

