(e.g., reading forum posts) will be used to model threaded engagement networks between users. We will use these structures to describe types of users (e.g., discussion starters, contributors, lurkers), their location within the network (e.g., centrality), the frequency of exchanges between users (e.g., reciprocity), and presence of subgroups (e.g., cliques). Core social network metrics will be computed at the participant-level (e.g., centrality; popularity), as well as by stigma-related topic (e.g., trending, liked). We will use these network parameters to model (1) user engagement in HMP and (2) changes in HIV care continuum outcomes. We will use the general framework of generalized linear mixed models^{101–103} (GLMM) to model these longitudinal outcome trajectories. 110-112 Given that some of our outcomes are binary, some count and some continuous traits they will be treated differently (identity for continuous outcome, logit for binary outcome and natural log for count outcomes). We will use the estimated network parameters as covariates in our models, measuring how network characteristics are associated in differences in outcomes across the two treatment groups. In addition, GLMM also allows us to link YBLMT's individual trajectories with social network changes by adding them as time-varying covariates. For example, one analysis will examine how changes in networks' characteristics effect changes in YBLMT's VS, after adjusting for changes in stigma. These follow a network autocorrelation metric, whereby a term is added to the general model to captures a (weighted) average of peers' outcomes. Exploratory analyses will determine if random effects should be included. Maximum likelihood estimation will be used for fixed effects. To ensure robustness, we will also apply an exchangeable working correlation structure to its corresponding generalized estimating equation model. 104

Note: Any deviations from the analysis plans outlined above or in the sections that follow will be documented and justified in the Statistical Analysis Plan developed for this protocol.

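### Stigma is compared with control by arm-only logistic regression; if it is scored as a scale, a baseline-adjusted score model would be more precise

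*Combined protocol and SAP*

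**What the plan says.** Hypothesis A (Section 2.3) states that participants given HMP Stigma "will report greater reductions in stigma" than those given information only. The Study Abstract sets the schedule: "Behavioral assessments will occur at baseline, 3, 6, 9 and 12 months".

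The comparison with control is in Section 10.3.1 (Specific Aim 1). The secondary analyses there cover "stigmarelated (e.g., reduction in HIV-related stigma) outcomes, using a logistic regression with group assignment on the model", and the stated reason for leaving out covariates is that randomisation is assumed to have produced balance. For Aim 1 in general, "Logistic regression analyses will be stratified by serostatus".

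Two other parts of the plan model stigma or allow continuous outcomes:

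- Section 10.3.2.1 (Aim 2) uses structural equation modelling to "test whether engagement with stigma content predicts changes in stigma-related outcomes over time", and splits total effects into direct and indirect parts.
- Section 10.3.3 (Aim 3) uses generalised linear mixed models with "identity for continuous outcome, logit for binary outcome and natural log for count outcomes", with the purpose of "measuring how network characteristics are associated in differences in outcomes across the two treatment groups".

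Section 5.4.4 says of Table 2 that "we include a summary of the primary and secondary outcomes". That table and the attached surveys are not in the text available.

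**The concern.** A logistic model needs a categorical outcome, and the example given, a reduction, points to a yes/no split of change from baseline. If the underlying measure is a score, precision is lost twice. Cutting the change at a threshold ignores how far each person moved. Using change without the baseline score as a covariate also leaves in variance that the baseline score would remove.

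The plan's justification, balance by randomisation, addresses bias. Baseline adjustment improves precision even when the arms are perfectly balanced.

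Stigma is the intervention's stated target. A moderate true effect on stigma scores could be missed because of how the outcome is coded, although the scores needed to avoid this are already collected.

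**Working it through.** The plan gives no power, standard deviation, correlation or cut-point for stigma, so there is no figure of its own to reproduce.

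**Inputs from the plan.** 150 per randomised arm (Section 3.2); 20% loss to follow-up and two-sided alpha 0.017 (Section 10.2, both stated for the primary outcome).

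**Assumed inputs.** Correlation rho between baseline and 12 months; share p of controls counted as reduced; standardised effect d = 0.3 for the power figures; equal variances; one follow-up time; independent, randomised participants only (referred Arm 2 peers are excluded).

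**Information kept, normal scores, small effects.** Relative to ANCOVA on the score:

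- Unadjusted change instead of ANCOVA keeps (1 − rho²) / [2(1 − rho)] = (1 + rho)/2. This is 0.60, 0.75 and 0.90 at rho = 0.2, 0.5 and 0.8.
- Cutting the change at a threshold keeps φ(z_p)² / [p(1 − p)]. At p = 0.2 this is 0.280²/0.16 = 0.490; at p = 0.5 it is 0.399²/0.25 = 0.637.
- The product at the low end (p = 0.2, rho = 0.2) is 0.490 × 0.60 = 0.294. At the high end (p = 0.5, rho = 0.8) it is 0.637 × 0.90 = 0.573.

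So 29 to 57% is kept, which means the yes/no outcome needs 1/0.294 = 3.4 to 1/0.573 = 1.75 times as many participants. Simulation agreed: 0.302 against 0.294 at the low end and 0.567 against 0.573 at the high end.

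**Power at d = 0.3, normal scores, any fall counted as reduced (50% of controls).** The change has standard deviation √[2(1 − rho)]. At rho = 0.5 this is 1, so the intervention proportion is Φ(0.3) = 0.618 against 0.500. The log odds ratio is 0.481 with standard error 0.234, so z = 2.05. ANCOVA gives z = 0.3 / √[2(1 − 0.25)/150] = 3.00. Efficiency is (2.05/3.00)² = 0.47.

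| rho | Efficiency | 150/arm, alpha 0.017: yes/no v ANCOVA | 120/arm, alpha 0.017 | 150/arm, alpha 0.05 |
|---|---|---|---|---|
| 0.3 | 41% | 26% v 63% | 20% v 52% | 41% v 78% |
| 0.5 | 47% | 37% v 73% | 29% v 62% | 54% v 85% |
| 0.6 | 50% | 46% v 80% | 37% v 70% | 63% v 90% |
| 0.7 | 52% | 60% v 90% | 49% v 81% | 75% v 95% |

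Both alphas are shown because 0.017 is attached to the primary comparisons and none is stated for secondary outcomes.

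**Other score shapes (simulation, d = 0.3, 150 per arm, rho 0.3 to 0.7).**

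- Skewed integer score, 0 to 15: efficiency 0.396 to 0.534.
- Coarse 1 to 5 score: 0.375 to 0.482. For these two, rho and d are on the underlying normal scale.
- Heavy tails, any fall counted: about 0.60 to 0.74 with t tails on 5 df and about 0.68 to 0.84 on 4 df. With 5 df and alpha 0.017, power was about 40% v 65%, 55% v 73% and 78% v 89% at rho = 0.3, 0.5 and 0.7.

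The size of the loss depends on the shape of the scores, but its direction did not change in any case.

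**The case against.** The strongest reply is that the point rests on material that cannot be seen. Scale scoring is inferred. Several instruments in the reference list are scales, for example one of internalised AIDS-related stigma, but a citation does not show use. The note closing Section 10.3.3 also refers to a Statistical Analysis Plan in which deviations will be recorded. This stands, and it is why the point is conditional on scale scoring. A reader might infer that the cut and the visit are undefined. The documents do not support that, because Table 2 may define them. A defined cut would still discard information.

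A reader might also infer that nothing else in the plan estimates an arm effect on stigma. That goes too far. Aim 2 concerns mediation of intervention effects, and its structural model may carry an arm effect on stigma. It is not, however, stated as the test of arm against control. Aim 3 does allow an identity link for continuous outcomes, but it is directed at the two intervention versions.

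A third reply is that a responder proportion is a legitimate estimand, in keeping with the binary primary outcome, and that stigma against control is a secondary comparison with no power claim. This is fair. It limits the weight of the point but does not remove the gain available from data already collected.

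Finally, 29 to 57% holds only under normality. The heavy-tailed results fall outside that range, so it should not be read as a general figure.

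**Conclusion.** The concern holds as a matter of precision. The only clearly stated comparison of stigma with control is an arm-only logistic regression. If stigma is scored as a scale, that analysis keeps about 29 to 57% of the information in a baseline-adjusted 12-month score under normality (rho 0.2 to 0.8, 20 to 50% of controls reduced). It keeps about 60 to 84% with t tails on 4 to 5 df (any fall counted, d = 0.3, rho 0.3 to 0.7). All of these inputs are assumptions, and the figures apply to randomised participants only.

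Two stronger readings are not supported. A reader might infer that the stigma comparison is biased; the calculation shows lost precision, not bias. A reader might also infer that the power statement in Section 10.2 is undermined. That statement concerns engagement in care and makes no claim about stigma, so nothing here contradicts it. The change is worth making, for a secondary outcome, with medium confidence until Table 2 is checked.

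**What to change.** In Section 10.3.1, for stigma measures scored as scales, compare each arm with control within serostatus by a linear mixed model of the 3-, 6-, 9- and 12-month scores adjusted for the baseline score, with the 12-month arm contrast as the estimate. ANCOVA at 12 months is a simpler alternative. Keep any proportion with reduced stigma as a supportive analysis.

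The cost is SAP wording, with no new data or visits. The estimate becomes a mean difference in score instead of an odds ratio. Measures that prove very skewed or have few categories need a model check, for example against an ordinal model adjusted for baseline. If Table 2 shows that a measure is not a scale score, the change does not apply to it.
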